9.0 Adverse Events

- 9.1 Toxicity of steroids will be recorded.
- 9.2 The more common side effects are:
 - headache
 - nausea and vomiting
 - weight gain.
 - confusion, excitement, and restlessness.
 - swelling of ankles, feet, or hands.
 - skin problems, such as acne, thin skin, and shiny skin.
 - increased thirst.
 - Infection
 - Hyperglycemia
 - Gastrointestinal bleeding

Hypertension (increased blood pressure)

10.0 Primary Response Criteria for patients receiving methylprednisolone

10.0.1 Clinical complete response criteria require all the following:

10.0.1.1	No need for ventilatory support at any point
10.0.1.2	Not oxygen dependent by day 28 of registration
10.0.1.3	Alive by day 28 from registration on trial
10.0.1.4	CT chest with minimal or no evidence of disease by day 28
	from registration

10.0.2 Clinical partial response criteria require that 2 of the following be present by day 14 of therapy:

10.0.2.1	No need for ventilatory support at any point
10.0.2.2	Not oxygen dependent by day 28 from registration on trial
10.0.2.3	CT chest stable to improve over baseline by day 28 from
	registration

10.1 Secondary Response Criteria:

- 10.1.1 Decrease of at least 25% in anyone of the following markers, if elevated at baseline: IL-6, ferritin, D-dimer, CRP or LDH by day 14
- 10.1.2 Improvement of absolute lymphocyte count in those presenting with lymphopenia. Improvement is defined as increase by 25 % or more by day 14.

11 Data Management

- 11.1 Patients will be registered after obtaining signed consent form.
- 11.2 Registration will be performed at Auxilio Mutuo by calling [contact] [name].

12 Statistical Analysis

- 12.0 Analysis will focus in comparing pre-treatment and post treatment values.

 Results will be analyzed using the intent to treat principle which in this case means that those cases who receive at least one dose of methylprednisolone will be considered evaluable.
- **12.1** Evaluable cases are considered as those who have clinical data for at least 1 subsequent day.
- 12.2 Due to the small sample size, non-parametric tests for matched data will be used.

13.0 REFERENCES:

- 1. Gautret, P., et al., *Hydroxychloroquine and azithromycin as a treatment of COVID-19:* results of an open-label non-randomized clinical trial. Int J Antimicrob Agents, 2020: p. 105949.
- 2. Chen, L., et al., *Convalescent plasma as a potential therapy for COVID-19.* Lancet Infect Dis, 2020. **20**(4): p. 398-400.
- 3. Carr, A.C., A new clinical trial to test high-dose vitamin C in patients with COVID-19. Crit Care, 2020. **24**(1): p. 133.
- 4. Zhou, F., et al., Clinical course and risk factors for mortality of adult inpatients with COVID-19 in Wuhan, China: a retrospective cohort study. Lancet, 2020. **395**(10229): p. 1054-1062.

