3.0 Background and Rationale

The management of Covid-19 with mild manifestations has usually been conservative. Traditionally, treatment has consisted of observation at home provided there is no shortness of breath or evidence of pneumonia. Front line therapy with Hydroxychloroquine (Plaquenil) combined with Azithromycin has been used with preliminary positive results[1]. Plasma therapy has been successfully used in a small number of cases[2]. Vitamin C has also been utilized, although no definitive results are available[3].

Covid-19 is a triphasic disorder typified by a first infectious phase that lasts from the first onset of symptoms until 7-10 days later when it is followed by a second phase considered as the inflammatory or pulmonary phase with appearance of lung infiltrates which is later followed by a hyperinflammation phase characterized by Acute Respiratory Distress Syndrome (ARDS), shock and cardiac failure. For unclear reasons, patients do not always proceed to develop the second or third phase and are spontaneously cured after the first phase. Figure 1

Figure 1

Basics of COVID19 infections

[figure not shown]

5 Siddiqi & Mehra, J Heart Lung Transpl (2020). Epub ahead of print: https://doi.org/10.1016/j.healun.2020.03.012

This second phase is heralded by an elevation of certain serologic markers of inflammation such as IL-6, CRP, LDH and ferritin as well as D-dimers[4, 5]. See figure 2

It is not clear why some patients enter this second phase of the disease while others do not, but what is clear is that the second or inflammatory phase is caused by pulmonary macrophage activation with subsequent release of the inflammatory mediators. These molecules will damage the capillary-alveolar membrane eventually causing respiratory insufficiency. These are the patients that frequently will require ventilatory support and eventually most will die. This second and third phase are in great part due to activation of the patient's immune system while the first phase is mostly mediated by the viral infection itself.

Figure 2 *

*Red line represents patients who died while blue line represents survivors. The x axis represents number of days after onset of illness.

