Usually anti-inflammatory therapy with an anti-IL-6 antibody, Tocilizumab, is reserved for patients who are evolving poorly, especially patients with severe pneumonia with elevated IL-6 serum levels [6]. However, once these patients have pneumonia, anti-inflammatory treatment is usually not very successful. Nevertheless, the use of methylprednisolone has been associated with substantial reduction of risk of death even if administered late, when patients already have ARDS[7]. However, if given late, the probability of dying is 52%[7].

[name], from Hospital Peset, in Valencia, Spain has developed an approach designed to anticipate the second, or so-called inflammatory phase. He has proposed that when the pulmonary infiltrates appear, this is no longer an infectious process, but it is purely an inflammatory or immune issue which causes anatomical injury to the capillary alveolar membrane resulting in respiratory distress. He uses corticosteroid therapy starting on the sixth day of the onset of symptoms, given for 5-7 days, with the goal of preventing the inflammatory phase. Steroids are used specifically to treat those cases who on day 6 are febrile and show elevation of serologic inflammatory markers without advanced radiologic pulmonary manifestations. His initial results reportedly are excellent and admissions to the intensive care unit decreased, with shortened hospital stays and radiological and favorable clinical evolution that he has described as "spectacular" (personal communication)

In Spain and Italy this approach is gaining acceptance but at present time it is not considered standard of care. The use of steroids has been criticized because there is no evidence from randomized clinical trials to support its use for COVID-19. In addition, the anti-inflammatory medications, may delay the elimination of virus and increase the risk of secondary infection.

However, there is no evidence that, as proposed by [name], a short course of steroids given shortly before the second phase of the disease to patients at high risk of entering the inflammatory phase, has had any unfavorable impact on the disease. Thus, the concern against its use is totally based on theoretical grounds. The few data available against the use of steroids come from trials in which they have used them either too late or too early[8].

[figure not shown]

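### The Section 10 response lists count a patient who worsens on methylprednisolone, starts tocilizumab and recovers as a responder, and count marker changes first seen after tocilizumab or plasma (low priority)

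*Protocol*

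**What the plan says.** Section 10 of the Protocol, headed as applying to the patients given methylprednisolone, fixes four response rules:

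- **10.0.1, complete response:** "Clinical complete response criteria require all the following". The four items are no ventilatory support, not oxygen dependent by day 28, alive at day 28, and a clear or nearly clear chest CT by day 28.
- **10.0.2, partial response:** "Clinical partial response criteria require that 2 of the following be present by day 14 of therapy". The three items cover ventilation, oxygen and CT.
- **10.1.1, markers:** "Decrease of at least 25% in anyone of the following markers, if elevated at baseline", with IL-6, ferritin, D-dimer, CRP and LDH listed and day 14 as the limit.
- **10.1.2, lymphocytes:** "Improvement of absolute lymphocyte count in those presenting with lymphopenia", meaning a rise of 25% or more by day 14.

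Three other places bear on later therapy. Section 7.7 excludes anyone on tocilizumab or plasma. Section 6.7 lists the drugs allowed alongside and names neither. Section 12.0 invokes intent to treat and explains it as meaning that "those cases who receive at least one dose of methylprednisolone will be considered evaluable".

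Section 3.0 says that tocilizumab usually "is reserved for patients who are evolving poorly, especially patients with severe pneumonia with elevated IL-6 serum levels". On plasma it says: "Plasma therapy has been successfully used in a small number of cases".

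**The concern.** None of the four rules asks what was given after methylprednisolone. By the Protocol's own account, tocilizumab goes to patients who are doing badly, so starting it after the steroid tends to mark worsening. If such a patient then recovers without ventilation, Section 10 records a response among the methylprednisolone patients.

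The marker rules have a related weakness. Secondary objective 2 asks whether markers improve after corticosteroids. A fall first seen after another anti-inflammatory drug, or after plasma, does not answer that.

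The study is non-randomized, and its untreated patients are those who did not meet the high-risk criteria. No comparable untreated group carries the same rescue use, so nothing offsets the effect. What is at stake is how the Section 10 rates are read, not the trial's stated success decision.

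**Working it through.** **Step 1: can the text produce this result?** The Protocol derives no figure for these criteria, so the main check is textual.

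| Place | What it settles | What it leaves open |
|---|---|---|
| 7.7 | Tocilizumab or plasma bars entry | A start after the first methylprednisolone dose |
| 6.7 | Drugs allowed alongside; neither is listed | Any consequence for scoring if one is given |
| 12.0, 12.1 | Who is evaluable: one dose, and data for one later day | How an evaluable patient is scored |
| 10.0.1, 10.0.2 | Ventilation, oxygen, CT; survival in 10.0.1 only | Later therapy |
| 10.1.1, 10.1.2 | A 25% change by day 14 | Later therapy |

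Take a treated patient who worsens, starts tocilizumab, is never ventilated, and at day 28 is alive, off oxygen and has a near-clear CT. All four items of 10.0.1 are met, and no other section removes the patient or changes the score. The result is a complete response.

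**Step 2: when are the marker rules exposed?** Only when the new therapy starts before the day 14 sample. Section 2.2 schedules markers at illness day 7-10 and then at days 14 and 28 from registration. Section 6.4 allows treatment no earlier than illness day 7, so the day 7-10 sample will often be the baseline. Day 14 is then the first scheduled post-dose value, and a pre-rescue value will often not exist.

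**Step 3: does it reach the success rule?** Section 5.4 counts respiratory failure, defined in Section 4.0 as O2 saturation below 91% or pO2 below 60 on room air. If that threshold is crossed before tocilizumab or plasma starts, the failure is already counted. Only a start before the threshold could matter.

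**Step 4: illustrative size for 10.0.1.** The inputs are r, the share of treated patients starting tocilizumab, and c, the share of those who still meet 10.0.1. Both are assumed. The planned number treated is 40-60 (Section 5.2).

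Shift in complete response rate, against scoring these patients as non-responders = r × c.

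| r | c | Shift (points) | Patients of 40 | Patients of 60 |
|---|---|---|---|---|
| 5% | 10% | 0.5 | 0.2 | 0.3 |
| 10% | 25% | 2.5 | 1.0 | 1.5 |
| 10% | 50% | 5.0 | 2 | 3 |
| 20% | 50% | 10.0 | 4 | 6 |
| 20% | 100% | 20.0 | 8 | 12 |

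For scale, the standard error of a 50% rate is √(0.25/40) = 7.9 points at n = 40 and √(0.25/60) = 6.5 points at n = 60. The 5-point example is below one standard error; the last two rows are above it. The last row is an extreme in which every patient who starts tocilizumab recovers. Section 3.0 says "once these patients have pneumonia, anti-inflammatory treatment is usually not very successful", which argues against values of c near 100% but supplies no figure for c.

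The direction needs no assumption: moving these patients to non-response can only remove responders.

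**The case against.** **An SAP, not shown here, could handle rescue therapy.** It could, and silence on scoring alone would be no finding. But the Protocol itself fixes the response definitions as closed lists. An SAP that scored rescued patients as failures would be changing those definitions.

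**Scoring the observed outcome whatever follows is a legitimate treatment-policy choice and fits intent to treat.** It would be legitimate if stated. Section 12.0 explains intent to treat as evaluability, which sets the denominator and not the score. The argument does justify continuing to report the rate as written.

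**Attribution is already weak.** Section 6.7 allows remdesivir, colchicine and several other drugs alongside, so reclassifying tocilizumab starters would not make the rate attributable to methylprednisolone. This stands. The narrower point survives: the Protocol links tocilizumab to a poor course, so its start carries information about how the steroid did.

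**A reader might infer more than the text supports, in three ways:**

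- *That the trial's success decision is inflated.* Step 3 shows that 5.4 and primary objective 1 are exposed only to therapy started before the oxygen threshold. Section 4.0 lists no complete or partial response objective.
- *That plasma recipients should also count as failures.* The Protocol gives no sign that plasma marks worsening; it mentions only successful use in a few cases. For plasma the issue is attribution alone.
- *That post-rescue marker values should be dropped.* Given the sampling schedule, many rescued patients would become automatic non-responders, and day 14 values would be lost from the matched analysis planned in 12.0 and 12.2.

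**Conclusion.** The point holds in limited form. As written, 10.0.1 and 10.0.2 count a patient who worsens, starts tocilizumab and recovers without ventilation as a responder. Sections 10.1.1 and 10.1.2 count a day 14 change first seen after tocilizumab or plasma. Against non-responder scoring the response rate moves upward only.

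The size cannot be determined. The 0.5 to 20 points shown for complete response rest wholly on assumed rescue and recovery shares. Later use could be near zero, since both therapies are barred at entry and absent from the allowed list. No comparable figure is offered for 10.0.2, 10.1.1 or 10.1.2. With the 5.4 decision largely untouched, priority is low.

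**What to change.** - **Data:** record the start date of any tocilizumab or plasma given after the first methylprednisolone dose.
- **10.0.1 and 10.0.2, tocilizumab:** score a patient who starts it after the first methylprednisolone dose and before the response assessment (day 28 at the latest) as a non-responder. Report the rate as currently written beside it.
- **10.0.1 and 10.0.2, plasma:** report the response rate both ways, without mandating failure.
- **10.1.1 and 10.1.2:** keep all observed day 14 values in the main paired analysis. Add a sensitivity analysis in which a change first seen after tocilizumab or plasma does not count.
- **5.4:** leave it unchanged. Report beside it the number who started either therapy before O2 saturation fell below 91% or pO2 below 60.

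This alters scoring and reporting only, not who may receive these therapies. The cost is a few sentences, one date field per therapy, a little more analysis work and a slightly less favourable response rate.

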2.0 Schedule of Study Assessments

- 2.1 At, or prior to, entry into study:
 - 2.1.1 History and Physical exam
 - 2.1.2 Labs: CBC, CMP, LDH, arterial blood gases, serum IL-6, serum ferritin, CRP, D-dimers, troponin
 - 2.1.3 Radiologic studies: CT chest without IV contrast preferably prior to treatment with methylprednisolone.
 - 2.1.4 Other studies:
 - 2.1.4.1 Either PCR for molecular detection of SARS-Cov-2 virus and serologic rapid test (IgG, IgM), or both (see figure 2). Cases who are IgG positive but IgM negative, will not be considered eligible unless they are positive by molecular PCR test or they are acutely ill with symptoms typical of Covid-19 (see section 6.2 for typical symptoms).
 - 2.1.4.2 O₂ saturation by pulse oximetry
 - 2.1.4.3 Influenza rapid test if considered necessary.
- 2.2 During study (only applies to those eligible for treatment with methylprednisolone):
 - 2.2.1 For patients admitted to hospital: Vital signs q 8 hours (not q 4 hrs) to reduce chance of nursing staff contamination
 - 2.2.2 Day 7-10 from first symptom of illness: CBC, CMP, LDH, serum IL-6, serum ferritin, CRP, d-dimers
 - 2.2.3 Day 14 from registration on trial:

- 2.2.3.1 repeat CBC, CMP, LDH, serum IL-6, serum ferritin, CRP, d-dimers
- 2.2.3.2 repeat PCR for molecular detection of SARS-Cov-2 virus
- 2.2.4 Day 28 from registration on trial:
 - 2.2.4.1 repeat CBC, CMP, LDH, serum IL-6, serum ferritin, CRP, d-dimers
 - 2.2.4.2 repeat PCR for molecular detection of SARS-Cov-2 virus
 - 2.2.4.3 CT chest without IV contrast

[figure not shown]

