4.0 Study Objectives and End Points

Primary Objective:

- 1- To decrease the rate of progression to hypoxemic respiratory failure in high risk patients with Covid-19, treated with prophylactic steroids during the first phase of the disease.
 - a. Hypoxemic respiratory failure is defined as:
 - 1. O_2 saturation of < 91% or pO_2 <60 on room air
- 2- To evaluate the rate of complications of patients observed without treatment.
 Complications include progression to respiratory failure or any other complication leading to hospitalization.

Secondary Objectives:

- 1. To determine % survival at 28 days from registration on this clinical trial
- 2. To determine if there is any improvement in inflammatory markers following treatment with corticosteroids.
- 3. To define the length of hospitalization
- 4. To determine the frequency of admissions to ICU.
- 5. To determine the percentage of patients who require ventilatory support.
- 6. To determine the rate of complications and progression to respiratory failure in patients with favorable features (i.e., those eligible for observation and not for therapy with methylprednisolone.)
 - a. To validate these results in an independent cohort of cases diagnosed as Covid-19 from our general hospital population.
- 7. We will evaluate the proportion of patients with clinical improvement, as defined by live discharge from the hospital, a decrease of at least 2 points from baseline on a modified ordinal scale (as recommended by the WHO R&D Blueprint Group), or both. [10]
 - 7.1 The six-point scale consists of the following categories:
 - (1) not hospitalized;

- (2) hospitalized, not requiring supplemental oxygen;
- (3) hospitalized, requiring supplemental oxygen;
- (4) hospitalized, requiring nasal high-flow oxygen therapy, noninvasive mechanical ventilation, or both;
- (5) hospitalized, requiring invasive mechanical ventilation, ECMO, or both; and
- (6) death.

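### The partial-response rule in Protocol 10.0.2 cannot be completed at its stated day 14, counts a ventilated patient who recovers as a responder, and omits survival

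*Protocol*

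**What the plan says.** Protocol section 10.0 sets clinical response criteria for patients given methylprednisolone.

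- **Complete response (10.0.1):** "Clinical complete response criteria require all the following". There are four items, among them freedom from ventilation and "Alive by day 28 from registration on trial".
- **Partial response (10.0.2):** "Clinical partial response criteria require that 2 of the following be present by day 14 of therapy". There are three items: "No need for ventilatory support at any point" (10.0.2.1), "Not oxygen dependent by day 28 from registration on trial" (10.0.2.2) and "CT chest stable to improve over baseline by day 28" from registration (10.0.2.3). Survival is not among them.

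The schedule in section 2.2 lists laboratory tests and PCR at day 14. The only CT after baseline is 2.2.4.3, under the heading "Day 28 from registration on trial". Section 8.3 starts treatment on day 1 to 3 of registration.

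The first primary objective in 4.0 is a different outcome: "To decrease the rate of progression to hypoxemic respiratory failure in high risk patients with Covid-19". Section 5.4 judges the treatment successful if no more than 50% of high-risk patients develop respiratory failure.

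**The concern.** A response rule needs one assessment time, and its items must be observable at that time. Here the heading of the rule and two of its three items carry different dates, counted from different starting points. Two people classifying the same patient could each follow the text and disagree, and the choice between readings could be made after outcomes are known.

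The rule also treats its items as interchangeable. Ventilatory support is a bad outcome that the trial counts separately (4.0, secondary objective 5), yet a good oxygen status and CT at day 28 can offset it. Survival is a condition of complete response and is absent from partial response. The reported partial-response rate could therefore include patients whom few readers would call responders. The study has no control arm and expects only 40 to 60 treated patients, so a few such classifications would be visible in the rate.

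**Working it through.** The plan attaches no target rate, sample size or test to partial response, so there is no stated figure to reproduce. The check is logical.

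**Inputs.** V = never ventilated (10.0.2.1, no day attached). O = not oxygen dependent (10.0.2.2, day 28). C = CT stable or improved (10.0.2.3, day 28). A = alive at day 28 (10.0.1.3, complete response only). The rule is read as at least 2 of V, O and C.

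**Step 1: can the rule be completed at day 14?**

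| Pair | Dates of the items | Complete at day 14 as written? |
|---|---|---|
| V + O | any point; day 28 | No |
| V + C | any point; day 28 | No |
| O + C | day 28; day 28 | No |

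Every pair contains at least one item dated day 28. Oxygen status could be observed at day 14, although the item is not defined there. The CT could not, because none is scheduled before day 28.

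**Step 2: do the clocks agree?** The heading counts from therapy and the items count from registration. If the first treatment day is therapy day 1 and falls on registration day s, then therapy day 14 is registration day s + 13. For s = 1, 2, 3 this gives registration day 14, 15 or 16.

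**Step 3: who qualifies?** There are 2 × 2 × 2 × 2 = 16 yes/no patterns of V, O, C and A. The condition V + O + C ≥ 2 holds in 8 of them:

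| | Alive at day 28 | Dead by day 28 | Total |
|---|---|---|---|
| Never ventilated | 3 | 3 | 6 |
| Ventilated | 1 | 1 | 2 |
| Total | 4 | 4 | 8 |

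These are counts of logical patterns, not probabilities.

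- *Ventilated and alive (1 pattern).* V = no, O = yes, C = yes. Items 10.0.2.2 and 10.0.2.3 are met as worded, so the patient is a partial responder. No interpretation is needed.
- *Dead by day 28 (4 patterns).* These qualify formally because A is not in the rule. If a patient who died has no usable CT (C = no), only one pattern remains: never ventilated and scored as not oxygen dependent.

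**Step 4: what does the death path depend on?** If the day-28 wording of the items governs, an unventilated death counts only if death is scored as not oxygen dependent, or if an earlier CT is accepted for the CT item. If the day-14 heading governs, a patient who is unventilated and off oxygen at day 14 and then dies before day 28 can count. The protocol rules out neither.

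**Step 5: weight of one patient.** With the 40 to 60 treated patients expected in 5.2, one reclassified patient changes the rate by 1/60 = 1.7 to 1/40 = 2.5 percentage points. The documents do not allow an estimate of how many patients would be affected.

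**Step 6: effect of the repair.** Requiring A and V, plus O or C, leaves 3 of the 8 patterns: exactly those alive and never ventilated.

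**The case against.** The strongest reply is that nothing decisive rests on this rule. The primary objective in 4.0 and the only success threshold, in 5.4, both use respiratory failure. That stands: a reader might infer that the trial's stated verdict is compromised, and it is not.

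A reader might also infer that the protocol has two rival primary endpoints, because 10.0 is headed as primary. The documents do not establish this. Section 10.1 sets secondary response criteria based on laboratory markers, so the labels may only rank clinical response above laboratory response. The labelling is loose and deserves a clarifying sentence.

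It is tempting to say outright that a patient who died counts as a responder. The text does not go that far. Being off oxygen is ordinarily said of a living, assessable patient, survival at 28 days is reported separately, and a statistical analysis plan could fix how deaths are scored. What stands is that 10.0.2 drops a condition that 10.0.1 includes and does not exclude the case.

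Finally, one might object to a patient who is still on oxygen at day 28, with a stable CT and no ventilation, counting as a partial responder. That is a plausible meaning of partial, since complete response already requires being off oxygen. It is not a defect of the rule.

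None of these replies removes the date conflict or the ventilated responder. Both follow from the protocol's own wording, not from detail left to a later document.

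**Conclusion.** The rule in 10.0.2 is wrong as written, in three respects of differing certainty.

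1. **Timing: certain.** No pair of items can be completed at the stated day 14, and the therapy and registration clocks can differ by up to two days.
2. **Ventilated responders: certain.** A patient who was ventilated and recovered qualifies through the oxygen and CT items.
3. **Survival: a real gap, conditional in effect.** An unventilated death by day 28 is not excluded. Whether it counts depends on the scoring of oxygen status after death, on whether an earlier CT is accepted, or on which date governs.

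The size can be stated only per patient, at about 1.7 to 2.5 points of the response rate for 60 to 40 treated. Any total would need counts of ventilated survivors and unventilated deaths that the documents do not give. The conclusion assumes that the rule means at least two items and, for the clock comparison, that the first treatment day is therapy day 1. The damage is confined to the partial-response endpoint; the success rule in 5.4 is untouched.

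**What to change.** Amend section 10.0.2 as follows:

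- Use one assessment day and one clock. Day 28 from registration matches the dated items and the CT schedule. The sponsor should confirm that this is the intent, because a day-14 rule would need both items re-dated and a CT that the schedule does not contain.
- Require both survival to day 28 and no ventilatory support at any point.
- Require in addition at least one of: not oxygen dependent, or CT stable or improved.
- Add a sentence that response under section 10 supports, and does not replace, the primary endpoint of hypoxemic respiratory failure in 4.0.

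The cost is a change of wording. With assessment at day 28, no visit, test or patient is added. The partial-response rate will be lower, because ventilated patients no longer qualify and deaths are excluded explicitly.
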